### **7.2.3.2 Events of Clinical Interest**

Selected non-serious and serious adverse events are also known as Events of Clinical Interest (ECI) and must be reported to the Sponsor.

For the time period beginning when the subject provides documented informed consent until treatment allocation/randomization, any ECI, or follow up to an ECI, that occurs to any subject must be reported within 24 hours to the Sponsor if it causes the subject to be excluded from the trial, or is the result of a protocol-specified intervention, including but not

limited to washout or discontinuation of usual therapy, diet, placebo treatment or a procedure.

For the time period beginning at treatment allocation/randomization through 30 days following cessation of treatment, any ECI, or follow up to an ECI, whether or not related to the Sponsor's product, must be reported within 24 hours to the Sponsor, either by electronic media or paper. Electronic reporting procedures can be found in the EDC data entry guidelines. Paper reporting procedures can be found in the Investigator Trial File Binder (or equivalent).

Events of clinical interest for this trial include:

- a. an overdose of Sponsor's product, as defined in Section 7.2.1 - Definition of an Overdose for This Protocol and Reporting of Overdose to the Sponsor, that is not associated with clinical symptoms or abnormal laboratory results.
- b. an elevated AST or ALT lab value that is greater than or equal to 3X the upper limit of normal and an elevated total bilirubin lab value that is greater than or equal to 2X the upper limit of normal and, at the same time, an alkaline phosphatase lab value that is less than 2X the upper limit of normal, as determined by way of protocol-specified laboratory testing or unscheduled laboratory testing.\*

\*Note: These criteria are based upon available regulatory guidance documents. The purpose of the criteria is to specify a threshold of abnormal hepatic tests that may require an additional evaluation for an underlying etiology. The trial site guidance for assessment and follow up of these criteria can be found in the Investigator Trial File Binder (or equivalent).

#### **7.2.4 Evaluating Adverse Events**

An investigator who is a qualified physician will evaluate all adverse events with respect to the elements outlined in [Table 9](#). The investigator's assessment of causality is required for each adverse event. Refer to [Table 9](#) for instructions in evaluating adverse events.

An investigator who is a qualified physician will evaluate all adverse events according to the NCI Common Terminology for Adverse Events (CTCAE), version 4. Any adverse event which changes CTCAE grade over the course of a given episode will have each change of grade recorded on the adverse event case report forms/worksheets.

All adverse events regardless of CTCAE grade must also be evaluated for seriousness. Investigators need to document if an SAE was associated with a medication error, misuse, or abuse.

For studies in which multiple agents are administered as part of a combination regimen, the investigator may attribute each adverse event causality to the combination regimen or to a single agent of the combination. In general, causality attribution should be assigned to the combination regimen (i.e., to all agents in the regimen). However, causality attribution may be assigned to a single agent if in the investigator's opinion, there is sufficient data to support full attribution of the adverse experience to the single agent.

Table 9 Evaluating Adverse Events

An investigator who is a qualified physician, will evaluate all adverse events as to:

V4.0 CTCAE Grading	Grade 1	Mild; asymptomatic or mild symptoms; clinical or diagnostic observations only; intervention not indicated.
	Grade 2	Moderate; minimal, local or noninvasive intervention indicated; limiting age-appropriate instrumental ADL.
	Grade 3	Severe or medically significant but not immediately life-threatening; hospitalization or prolongation or hospitalization indicated; disabling; limiting self-care ADL.
	Grade 4	Life threatening consequences; urgent intervention indicated.
	Grade 5	Death related to AE
Seriousness	A serious adverse event is any adverse event occurring at any dose or during any use of Sponsor's product that:	
	† Results in death; or	
	† Is life threatening; or places the subject, in the view of the investigator, at immediate risk of death from the event as it occurred (Note: This does not include an adverse event that, had it occurred in a more severe form, might have caused death.); or	
	† Results in a persistent or significant disability/incapacity (substantial disruption of one's ability to conduct normal life functions); or	
	† Results in or prolongs an existing inpatient hospitalization (hospitalization is defined as an inpatient admission, regardless of length of stay, even if the hospitalization is a precautionary measure for continued observation. (Note: Hospitalization for an elective procedure to treat a pre-existing condition that has not worsened is not a serious adverse event. A pre-existing condition is a clinical condition that is diagnosed prior to the use of a MSD product and is documented in the patient's medical history.); or	
	† Is a congenital anomaly/birth defect (in offspring of subject taking the product regardless of time to diagnosis); or	
	Is a new cancer (that is not a condition of the study) (although not serious per ICH definition, is reportable to the Sponsor within 24 hours to meet certain local requirements); or	
	Is an overdose (whether accidental or intentional). Any adverse event associated with an overdose is considered a serious adverse event for collection purposes. An overdose that is not associated with an adverse event is considered a non-serious event of clinical interest and must be reported within 24 hours.	
	Other important medical events that may not result in death, not be life threatening, or not require hospitalization may be considered a serious adverse event when, based upon appropriate medical judgment, the event may jeopardize the subject and may require medical or surgical intervention to prevent one of the outcomes listed previously (designated above by a †).	
Duration	Record the start and stop dates of the adverse event. If less than 1 day, indicate the appropriate length of time and units	
Action taken	Did the adverse event cause the Sponsor's product to be discontinued?	
Relationship to Sponsor's Product	Did the Sponsor's product cause the adverse event? The determination of the likelihood that the Sponsor's product caused the adverse event will be provided by an investigator who is a qualified physician. The investigator's signed/dated initials on the source document or worksheet that supports the causality noted on the AE form, ensures that a medically qualified assessment of causality was done. This initialed document must be retained for the required regulatory time frame. The criteria below are intended as reference guidelines to assist the investigator in assessing the likelihood of a relationship between the test drug and the adverse event based upon the available information.  The following components are to be used to assess the relationship between the Sponsor's product and the AE; the greater the correlation with the components and their respective elements (in number and/or intensity), the more likely the Sponsor's product caused the adverse event (AE):	
	Exposure	Is there evidence that the subject was actually exposed to the Sponsor's product such as: reliable history, acceptable compliance assessment (pill count, diary, etc.), expected pharmacologic effect, or measurement of drug/metabolite in bodily specimen?
	Time Course	Did the AE follow in a reasonable temporal sequence from administration of the Sponsor's product? Is the time of onset of the AE compatible with a drug-induced effect (applies to trials with investigational medicinal product)?
	Likely Cause	Is the AE not reasonably explained by another etiology such as underlying disease, other drug(s)/vaccine(s), or other host or environmental factors

Relationship to Sponsor's Product (continued)	The following components are to be used to assess the relationship between the test drug and the AE: (continued)	
	Dechallenge	Was the Sponsor's product discontinued or dose/exposure/frequency reduced? If yes, did the AE resolve or improve? If yes, this is a positive dechallenge. If no, this is a negative dechallenge. (Note: This criterion is not applicable if: (1) the AE resulted in death or permanent disability; (2) the AE resolved/improved despite continuation of the Sponsor's product; or (3) the trial is a single-dose drug trial); or (4) Sponsor's product(s) is/are only used one time.)
	Rechallenge	Was the subject re-exposed to the Sponsor's product in this study? If yes, did the AE recur or worsen? If yes, this is a positive rechallenge. If no, this is a negative rechallenge. (Note: This criterion is not applicable if: (1) the initial AE resulted in death or permanent disability, or (2) the trial is a single-dose drug trial); or (3) Sponsor's product(s) is/are used only one time). NOTE: IF A RECHALLENGE IS PLANNED FOR AN ADVERSE EVENT WHICH WAS SERIOUS AND WHICH MAY HAVE BEEN CAUSED BY THE SPONSOR'S PRODUCT, OR IF REEXPOSURE TO THE SPONSOR'S PRODUCT POSES ADDITIONAL POTENTIAL SIGNIFICANT RISK TO THE SUBJECT, THEN THE RECHALLENGE MUST BE APPROVED IN ADVANCE BY THE SPONSOR CLINICAL DIRECTOR AS PER DOSE MODIFICATION GUIDELINES IN THE PROTOCOL.
Consistency with Trial Treatment Profile	Is the clinical/pathological presentation of the AE consistent with previous knowledge regarding the Sponsor's product or drug class pharmacology or toxicology?	
The assessment of relationship will be reported on the case report forms /worksheets by an investigator who is a qualified physician according to his/her best clinical judgment, including consideration of the above elements.		
Record one of the following	Use the following scale of criteria as guidance (not all criteria must be present to be indicative of a Sponsor's product relationship).	
Yes, there is a reasonable possibility of Sponsor's product relationship.	There is evidence of exposure to the Sponsor's product. The temporal sequence of the AE onset relative to the administration of the Sponsor's product is reasonable. The AE is more likely explained by the Sponsor's product than by another cause.	
No, there is not a reasonable possibility of Sponsor's product relationship	Subject did not receive the Sponsor's product OR temporal sequence of the AE onset relative to administration of the Sponsor's product is not reasonable OR the AE is more likely explained by another cause than the Sponsor's product. (Also entered for a subject with overdose without an associated AE.)	

## **7.2.5 Sponsor Responsibility for Reporting Adverse Events**

All Adverse Events will be reported to regulatory authorities, IRB/IECs and investigators in accordance with all applicable global laws and regulations, i.e., per ICH Topic E6 (R1) Guidelines for Good Clinical Practice.

## **7.3 TRIAL GOVERNANCE AND OVERSIGHT**

### **7.3.1 Scientific Advisory Committee**

This trial was developed in collaboration with a Scientific Advisory Committee (SAC). The SAC comprises both Sponsor and non-Sponsor scientific experts who provide input with respect to trial design, interpretation of trial results and subsequent peer-reviewed scientific publications.

## **8.0 STATISTICAL ANALYSIS PLAN**

This Section outlines the statistical analysis plan (SAP) strategies and procedures for the primary and key secondary analyses of the study. Exploratory and other non-confirmatory analyses will be outlined in a separate supplemental Statistical Analysis Plan (sSAP).

This study was developed in collaboration with a SAC. The SAC is comprised of both Sponsor and non-Sponsor scientific experts who provide scientific and strategic guidance on various aspects of the clinical trial and/or development, which may include study design, interpretation of study results, and subsequent peer-reviewed scientific publications.

Changes to analyses made after the protocol has been finalized, but prior to database lock, will be documented in the sSAP and referenced in the Clinical Study Report (CSR) for the study. Post hoc exploratory analyses will be clearly identified in the CSR.

### **8.1 Statistical Analysis Plan Summary**

This Section contains a brief summary of the statistical analyses for this trial. Full detail is found in the subsequent Sections.

Study Design Overview	Phase 1/1b Trial of MK-4280 as Monotherapy, in Combination with Pembrolizumab, in combination with Pembrolizumab and either mFOLFOX7, FOLFIRI or lenvatinib, and as a co-formulated product with pembrolizumab (MK-4280A) in Subjects With Advanced Solid Tumors. A 3+3 design in Part A to identify preliminary MTD; TPI design for dose confirmation and efficacy expansion cohorts for combination therapy (HNSCC and CRC), a randomized dose finding cohort (gastric cancer), MK-4280 monotherapy cohorts (CRC and gastric) and a MK-4280A cohort in Part B.
Analysis Populations	Safety (Primary): All-Subjects-as-Treated (ASaT) PK (Secondary): Per-Protocol (PP) Efficacy (Secondary & Exploratory): Full Analysis Set (FAS)
Primary Endpoint(s)	Safety: DLTs

Key Secondary Endpoints	PK parameters of single-agent MK-4280, MK-4280 in combination with pembrolizumab, in combination with pembrolizumab and either mFOLFOX7, FOLFIRI or lenvatinib, and as a co-formulated product with pembrolizumab; PK profile of pembrolizumab in combination with MK-4280 with or without mFOLFOX7, FOLFIRI or lenvatinib, and as part of MK-4280A  ORR measured by RECIST 1.1 as assessed by investigator review
Statistical Methods for Key Efficacy/Immunogenicity/ Pharmacokinetic Analyses	Serum concentrations of MK-4280 in each arm will be summarized by planned visit and time for each dose separately; PK parameters will be summarized by dose.  For each tumor type separately, the point estimate and 95% confidence interval (CI) for ORR will be evaluated in subjects treated with MK-4280 monotherapy, in combination with pembrolizumab (sequential administration and co-formulated product) or in combination with pembrolizumab and either mFOLFOX7, FOLFIRI or lenvatinib, using exact binomial distribution. A between dose comparison for ORR in the gastric combination therapy cohort will be conducted.
Treatment Assignment	In Part A, subjects are allocated to increasing doses of single-agent MK-4280 and MK-4280 coadministered with pembrolizumab without randomization centrally through IVRS; the study is open-label. In Part B Arm 2, subjects with gastric cancer will be randomized in a 1:1 fashion through IVRS to 1 of 2 doses of MK-4280 in combination with a fixed dose of pembrolizumab. Enrollment to Arm 3 or Arm 4 will be guided by a subject's eligibility for one arm or the other or, if eligible for both arms, will be determined by investigator choice. If any of Arms 1, 2C and 5 in Part B for 3L+ CRC subjects are enrolling at the same time, subjects will be assigned in an alternating fashion across the open arms at the study level through IVRS. Otherwise, all other subjects in Part B will receive the same treatment within their assigned arm and therefore will not be randomized; an IVRS will be used to control enrollment.
Statistical Methods for Key Safety Analyses	Summary statistics (counts, percentage, mean, standard deviation, etc.) will be provided for the safety endpoints as appropriate. The estimate of the DLT rate among subjects treated with the recommended MK-4280 Phase 2 dose when used in combination with pembrolizumab, and in combination with pembrolizumab and either mFOLFOX7, FOLFIRI or lenvatinib, and the 80% Bayesian Credible Interval for the estimate will be provided.
Interim Analyses	Safety will be monitored by cumulative data reviews throughout the trial. Data will be examined on a continuous basis to allow for dose-escalation decisions using the 3+3 design in Part A and dose-confirmation decisions using the TPI design in Part B. An interim analysis for efficacy will be performed for the CRC and PD-1-treatment-naïve HNSCC combination cohorts in Part B to determine tumor-specific cohort expansion to a maximum of 40 (HNSCC) or 100 (CRC) subjects. Safety and efficacy data will be monitored for the 2 different doses of MK-4280 administered with pembrolizumab in the gastric cancer cohort on a continuous basis to aid in internal decision making and to determine if an additional 20 subjects with gastric cancer will be enrolled to receive MK-4280 monotherapy at the RP2D.
Multiplicity	No multiplicity adjustment is planned in this Phase 1/1b study.

Sample Size and Power	The sample size of the dose escalation and dose confirmation/efficacy expansion (Parts A and B) depends on the observed DLT profiles of MK-4280 monotherapy and MK-4280 coadministered with pembrolizumab. A target sample size of 576 subjects will be used for study planning purposes.
-----------------------	---

## **8.2 Responsibility for Analyses/In-House Blinding**

The statistical analysis of the data obtained from this study will be the responsibility of the Clinical Biostatistics department of the Sponsor.

This trial is conducted as an open-label trial, ie, subjects, investigators, and Sponsor personnel will be aware of subject treatment assignments after each subject is enrolled and treatment is assigned.

## **8.3 Hypotheses/Estimation**

Objectives and hypotheses of the study are stated in Section 3.0.

## **8.4 Analysis Endpoints**

Efficacy and safety endpoints are listed below, followed by the descriptions of the derivations of selected endpoints.

### **8.4.1 Efficacy/Immunogenicity/Pharmacokinetics Endpoints**

Objective response rate in subjects treated with MK-4280 alone, in combination with pembrolizumab, or in combination with pembrolizumab and either mFOLFOX7, FOLFIRI or lenvatinib is a secondary endpoint of the trial and is defined as the proportion of subjects in the analysis population who experience complete response (CR) or partial response (PR) using RECIST 1.1 criteria as assessed by investigator review. Other efficacy endpoints (eg, Duration of Response [DOR], progression-free survival [PFS], Overall Survival [OS]) or the use of irRECIST 1.1 criteria are exploratory endpoints in this trial and will be defined in the sSAP.

Pharmacokinetic endpoints include serum concentrations of MK-4280, pembrolizumab, and lenvatinib, and derived PK parameters.

For the comparison of MK-4280 and pembrolizumab pharmacokinetics administered as a co-formulated product (MK-4280A, Cohort A, Arm 5) with that of its individual components administered sequentially (Cohort A, Arm 2C), the pharmacokinetic endpoints of interest are  $AUC_{0-21\text{days}}$  and  $C_{\max}$  from the first cycle. Additional PK parameters such as  $AUC_{0-\infty}$  and soluble LAG-3 exposure parameters such as  $AUC_{0-21\text{days}}$  from the first cycle administration of MK-4280A and MK-4280 administered in sequential combination with pembrolizumab are also of interest.

To characterize the pharmacokinetics in subjects from China, pharmacokinetic endpoints include serum concentrations of MK-4280 and pembrolizumab, and derived PK parameters:

- Single dose parameters:  $AUC_{0-21\text{days}}$ ,  $C_{\max}$ ,  $T_{\max}$ , and  $t_{1/2}$ .

- Multiple dose parameters:  $C_{trough}$ ,  $AUC_{0-21days}$ , and  $C_{max}$  at steady state, accumulation ratio.

#### **8.4.2 Safety Endpoints**

The primary safety endpoint is DLT. Safety will be monitored by cumulative data reviews throughout the trial. The toxicities and grades experienced by subjects who have received study treatment, including AEs and SAEs, will be summarized. Of particular interest are infusion related reactions and immune-related AEs. Other safety measures evaluated in all parts of the study include laboratory safety assessments, ECGs, vital signs, and physical examinations.

#### **8.4.3 Derivations of Safety Endpoints**

Description of safety measures is provided in Section 7.1.

### **8.5 Analysis Populations**

#### **8.5.1 Safety Analysis Populations**

The ASaT population will be used for the analysis of safety data in this study. The ASaT population consists of all subjects who received at least 1 dose of study treatment. In case of treatment administration errors, subjects will be analyzed according to the treatment they actually received. For DLT evaluation, ASaT subjects that were observed for safety for 21 days after the first dose of assigned treatment or experienced a DLT prior to 21 days after the first dose of assigned treatment will be used.

At least 1 laboratory or vital sign measurement obtained subsequent to at least 1 dose of study treatment is required for inclusion in the analysis of each specific parameter. To assess change from baseline, a baseline measurement is also required.

#### **8.5.2 Pharmacokinetic Analysis Populations**

The PP population will be used for the PK analyses and target engagement. The PP population consists of all subjects who comply with the protocol sufficiently to ensure that these data will be likely to exhibit the effects of treatment, according to the underlying scientific model. Compliance covers such considerations as exposure to treatment, availability of measurements and absence of major protocol violations. Major protocol violators will be identified to the extent possible prior to database lock by individuals responsible for data collection/compliance, and its analysis and interpretation. Any subjects or data values excluded from analysis will be identified, along with their reason for exclusion, in the CSR. At the end of the study, all subjects who are compliant with the study procedure as aforementioned and have available data from at least 1 treatment will be included in the analysis dataset.

#### **8.5.3 Efficacy Analysis Populations**

The FAS population will be used for the analysis of secondary and exploratory efficacy data in this trial. The FAS population consists of all subjects with a baseline scan with measurable

disease by investigator assessment who were administered a dose of study treatment regardless of dose level.

## **8.6 Statistical Methods**

This Section describes the statistical methods that address the primary and secondary objectives. Methods related to exploratory endpoints will be described in the sSAP.

### **8.6.1 Statistical Methods for Safety Analyses**

Safety and tolerability will be assessed by clinical review of all relevant parameters including AEs, SAEs, laboratory tests, vital signs, ECG measurements, and physical examinations.

Dose limiting toxicities will be listed, and DLTs and AEs will be summarized as counts and frequencies for each MK-4280 dose level administered as monotherapy, in combination with pembrolizumab, or in combination with pembrolizumab and either mFOLFOX7, FOLFIRI or lenvatinib that had at least 3 subjects treated and listed for other dose levels. The estimate of the DLT rate among subjects treated with the preliminary RP2D and the 80% Bayesian credible interval based on a prior distribution of Beta (1,1) for the estimate will be provided.

Laboratory assessments, vital signs, and other safety endpoints will be summarized as appropriate.

In addition, the broad clinical and laboratory AE categories consisting of the percentage of subjects with any AE, a drug-related AE, an SAE, an AE that is both drug-related and serious, and who discontinued due to an AE will be summarized for dose levels with at least 3 subjects treated and listed for other doses.

Data from subjects who experienced disease progression in the Part B monotherapy arm and crossed over into the combination arm will be presented separately.

Data from subjects in Arm 3, Arm 4 and Arm 6 will be summarized separately.

The difference and 95% CI for the rates of infusion related reactions and immune related AEs between MK-4280 administered as a co-formulated product with pembrolizumab (MK-4280A, Arm 5) and MK-4280 and pembrolizumab administered sequentially (Arm 2C, equivalent dose to Arm 5) will be calculated.

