#### 3.1 Primary Objective(s) & Hypothesis(es)

[figure not shown]
- 1) **Objective:** To determine the safety and tolerability of MK-4280 monotherapy (for subjects in Part A, Arm 1 and Part B, Arm 1) and to establish a maximum tolerated dose (MTD) or maximum administered dose (MAD)
- 2) **Objective:** To determine the safety and tolerability of MK-4280 in combination with pembrolizumab (for subjects in Part A, Arm 2 and Part B, Arm 2A, 2B and 2C) and to establish a preliminary recommended Phase 2 dose (RP2D) for combination therapy
- 3) **Objective:** To determine the safety and tolerability and to establish a preliminary RP2D of MK-4280 in combination with pembrolizumab and mFOLFOX7 (Arm 3) and of MK-4280 in combination with pembrolizumab and FOLFIRI (Arm 4) in subjects with MSS PD-1-treatment-naïve CRC that have received  $\leq 1$  line of prior therapy (Cohort B)
- 4) **Objective:** To determine the safety and tolerability of MK-4280 and pembrolizumab when administered as a co-formulated product (MK-4280A, Arm 5) and compare to the safety and tolerability of MK-4280 and pembrolizumab when administered sequentially (Part B subjects receiving MK-4280 800 mg plus pembrolizumab 200 mg Q3W, Arm 2C) (Cohort A)
- 5) **Objective:** To determine the safety and tolerability of MK-4280 and pembrolizumab when administered as a co-formulated product in subjects in China (MK-4280A, Arm 5, Cohort F)
- 6) **Objective:** To determine the safety and tolerability and to establish a preliminary RP2D of MK-4280 in combination with pembrolizumab and lenvatinib (Arm 6) in subjects with MSS PD-1-treatment-naïve CRC that have received 2 lines of prior therapy (Cohort G)

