#### **4.2.1.2 Rationale for MK-4280A – Co-formulated MK-4280 and Pembrolizumab**

MK-4280A is a single drug product containing a fixed dose combination of 800 mg MK-4280 and 200 mg pembrolizumab antibodies. The single formulation vial could provide significant benefit to subjects and providers, including simplified preparation and reduced infusion times compared to separate formulations. Data from Cohort A subjects enrolled in Part B, Arm 5 will be used to compare PK and safety parameters between sequentially administered (Part B, Arm 2C) and co-formulated (Part B, Arm 5) MK-4280 and pembrolizumab.

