#### **Rationale for MK-4280A in Chinese Subjects**

[figure not shown]
MK-4280A will also be evaluated in Chinese subjects from mainland China with advanced solid tumors (Arm 5, Cohort F). The purpose of this cohort is to characterize the PK and safety profile of MK-4280A in subjects in China. Data from this evaluation will be used to demonstrate acceptable safety and PK of MK-4280A in Chinese subjects and will be leveraged to support use of MK-4280A in China in future studies.

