#### **4.2.2.1.4 Rationale for MK-4280A Dose and Biocomparability Study**

The dose of MK-4280A will be comprised of 800 mg of MK-4280 and 200 mg of pembrolizumab. This dosing will allow for comparisons of Cohort A subjects in Arm 5 against subjects in Arm 2C of Part B receiving the sequential administration of 800 mg of MK-4280 and 200 mg of pembrolizumab.

Data collected from Cohort A subjects receiving sequentially administered MK-4280 + pembrolizumab (Arm 2C) will serve as a comparator to subjects from Cohort A receiving MK-4280A (Arm 5). Since 800 mg is a new dose of MK-4280 and no subjects on study that have yet received this dose, additional subjects in Cohort A to receive 800 mg MK-4280 and pembrolizumab (Arm 2C) were added to enable comparison.

The dose of MK-4280A will also allow for comparisons within Arm 5 of subjects in China (Cohort F) against subjects in the US (Cohort A).

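### Section 8.6.1 does not limit the Arm 5 versus Arm 2C safety contrast to Cohort A, and it names no separate safety summary for Cohort F

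*Combined protocol and SAP*

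**What the plan says.** All references are to the combined protocol and SAP; Section 8 is the SAP.

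**Objectives.** Primary objective 4 (Section 3.1) compares the safety of the co-formulated product in Arm 5 with sequential dosing, defined as "Part B subjects receiving MK-4280 800 mg plus pembrolizumab 200 mg Q3W, Arm 2C) (Cohort A". Primary objective 5 is "To determine the safety and tolerability of MK-4280 and pembrolizumab when administered as a co-formulated product in subjects in China", with Arm 5, Cohort F given as the group.

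**Rationale.** Section 4.2.1.2 says which subjects serve the comparison: "Data from Cohort A subjects enrolled in Part B, Arm 5 will be used to compare PK and safety parameters between sequentially administered" and co-formulated dosing. For the China cohort it says: "The purpose of this cohort is to characterize the PK and safety profile of MK-4280A in subjects in China".

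**Safety methods.** Section 8.6.1 sets up the contrast between "co-formulated product with pembrolizumab (MK-4280A, Arm 5) and MK-4280 and pembrolizumab administered sequentially (Arm 2C, equivalent dose to Arm 5) will be calculated". Its general tabulation is by dose level: "DLTs and AEs will be summarized as counts and frequencies for each MK-4280 dose level administered as monotherapy, in combination with pembrolizumab", or in a triplet. Crossover data are presented apart, and "Data from subjects in Arm 3, Arm 4 and Arm 6 will be summarized separately". Neither Arm 5 nor Cohort F is on that list.

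**PK and efficacy methods.** Sections 8.4.1, 8.6.4 and 8.9.4 each name Cohort A for the Arm 5 versus Arm 2C PK comparison. Section 8.6.3.2 sets Cohort F PK apart. Section 8.6.2 reports ORR separately for co-formulated and sequential dosing.

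**The concern.** Objective 4 asks about formulation: the same two antibodies at the same doses, given as one product or one after the other, within one cohort. The analysis sentence that serves it takes the whole of Arm 5, and Arm 5 contains a second population.

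Cohort F is recruited in mainland China, with any metastatic solid tumor and no more than two earlier lines of treatment. Cohort A is CRC that has progressed through all available standard therapy (Section 5.1.2). Cohort F goes only to Arm 5, outside the alternating assignment used when Arms 1, 2C and 5 enroll together (Section 5.3). It may also still be recruiting after the global portion has closed (Section 12.7.1). A difference in infusion-reaction or immune-related AE rates computed as written would therefore be partly a difference between populations.

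Objective 5 has a related gap. It is primary, it concerns Cohort F alone, and DLT is the primary safety endpoint (Section 8.4.2). Yet the safety methods contain no sentence that yields Cohort F results by themselves. Section 4.2.2.1.4 also says the dose allows "comparisons within Arm 5 of subjects in China (Cohort F) against subjects in the US (Cohort A"), which would need separate cohort results.

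**Working it through.** **1. The plan's own figures for these arms.** No figure is stated for the safety contrast. The nearest is the PK precision in Section 8.9.4, which uses 40 Arm 5 Cohort A subjects and 40 Arm 2C subjects. For MK-4280 AUC with SD 0.429:

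half-width = t(0.95, 78 df) × 0.429 × √(1/40 + 1/40) = 0.1597, against 0.159 stated (a third-decimal difference).

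The other three half-widths come to 0.1723, 0.1262 and 0.1481, against 0.172, 0.126 and 0.148. So the PK plan works on 40 versus 40, Cohort A only.

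The Part B maximum shows that Cohort F is counted in addition. By cohort, A to G: 200 + 68 + 40 + 20 + 100 + 20 + 68 = 516, as stated. Cohort A's 200 includes 40 for Arm 5, and Cohort F adds 20, so Arm 5 can reach 60.

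**2. The sections side by side.**

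| Place | Co-formulated group for the comparison with Arm 2C |
|---|---|
| Objective 4 | Arm 5, tagged Cohort A |
| 4.2.1.2 (PK and safety) | Arm 5, Cohort A |
| 8.4.1, 8.6.4, 8.9.4 (PK) | Arm 5, Cohort A |
| 8.6.1 (safety) | Arm 5 |

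The safety population in Section 8.5.1 takes everyone dosed, so it does not supply the missing limit.

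**3. Share and shift.** With p_A and p_F the event rates in Arm 5 Cohort A and Cohort F:

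whole-arm rate = (40·p_A + n_F·p_F)/(40 + n_F)

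shift in the contrast = [n_F/(40 + n_F)] × (p_F − p_A)

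- n_F = 20: share 20/60 = 0.333
- n_F = 10: share 10/50 = 0.20

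The documents give no event rates for these groups, so the gap p_F − p_A is assumed:

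| Assumed gap (points) | Shift, n_F = 20 | Shift, n_F = 10 |
|---|---|---|
| 0 | 0 | 0 |
| 10 | 3.3 | 2 |
| 20 | 6.7 | 4 |
| 30 | 10.0 | 6 |

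**4. Precision with and without Cohort F.** Section 8.6.1 names no interval method, so this uses the normal approximation with an assumed common rate p: half-width = 1.96 × √[p(1−p)(1/n₁ + 1/n₂)].

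| Assumed p | 40 vs 40 (points) | 60 vs 40 (points) |
|---|---|---|
| 5% | 9.6 | 8.7 |
| 10% | 13.1 | 12.0 |
| 20% | 17.5 | 16.0 |
| 30% | 20.1 | 18.3 |

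Restricting to Cohort A widens the interval by a factor of √[(1/40 + 1/40)/(1/60 + 1/40)] = √1.2, about 10%.

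**The case against.** The best reply is that the intent is already on the page. Section 8.6 says its methods address the objectives, objective 4 carries the Cohort A tag, and Section 4.2.1.2 says plainly that Cohort A subjects serve the safety comparison. Objective 4 itself labels the test arm as MK-4280A, Arm 5, and 8.6.1 may simply have reused that label. This stands as far as intent goes. A reader might infer that the sponsor plans to mix the two populations; the documents do not support that. What remains is that the sentence defining the analysis gives a different set from the objective it serves, while the parallel PK sentences give the right one.

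A reader might also infer from the dose-level tabulation that Arm 5 will be combined with Arm 2C, or left out of the tables. Section 8.6.1 says neither. Table layout is not specified there, its contrast already requires separate Arm 5 and Arm 2C rates for the two event types of special interest, and all DLTs are listed. DLT reviews are also required in Arm 2C (Section 5.2.2.2.5) and in Arm 5 Cohort A (Section 5.2.2.4). The narrower gap survives: nothing in 8.6.1 calls for Cohort F safety on its own. The supplemental SAP might settle this, but Section 8.0 reserves it for exploratory and other non-confirmatory work and keeps the primary analyses in Section 8.

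Third, the consequence is limited. There is no hypothesis testing (Section 8.7) and no multiplicity control (Section 8.8), and no decision rule uses this contrast. That stands, and it limits the weight of the point.

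Finally, the restricted contrast would still not isolate formulation. Arm 5 Cohort A is US-only, with no such limit stated for Arm 2C. Arm 5 opens only after ten Arm 2C subjects finish the DLT period, and alternation applies only while arms enroll together. That also stands; the restriction removes one known source of mixing and leaves these.

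**Conclusion.** The point holds as a specification gap in Section 8.6.1 with two parts.

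- The formulation safety contrast, as written, uses the wrong analysis set for primary objective 4. Up to one third of the Arm 5 side would come from Cohort F, and the estimate would move by up to one third of the Cohort F minus Cohort A rate gap.
- No separate Cohort F safety summary is named for primary objective 5, although the PK plan has one.

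The one-third share assumes that both Arm 5 cohorts fill; it falls to one fifth if Cohort F reaches only 10. The gap itself is unknown. If it is near zero the estimate hardly moves. Even an assumed 30-point gap shifts it by 10 points, against a half-width of 17.5 points at 40 versus 40 with an assumed 20% rate. A reader might infer that including Cohort F would create or hide a safety signal. The documents give no event rates from which to judge that, and the contrast is descriptive. The case for the change rests on agreement between objective and analysis, and on the low cost, rather than on a demonstrated effect on results.

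**What to change.** Two changes to Section 8.6.1:

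1. In the infusion-reaction and immune-related AE contrast, define the co-formulated group as Arm 5, Cohort A, compared with Arm 2C. This matches Section 8.6.4.
2. State that DLTs, AEs and the broad AE categories for Arm 5 Cohort F are summarized separately from Arm 5 Cohort A and from Arm 2C, in line with Section 8.6.3.2.

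This takes one or two sentences and a few table columns, with no new data. The cost is precision: groups of 40, 40 and up to 20, with the contrast interval about 10% wider than at 60 versus 40 under equal rates. The Cohort F rates in particular should be read descriptively, and the report should note the remaining region and timing differences between Arm 5 Cohort A and Arm 2C.
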